3.3 Analysis Populations

3.3.1 *Randomized Population*

All subjects who are randomized.

3.3.2 *Safety Population*

All subjects who have had at least one dose of study drug and one subsequent contact with the Investigator will be analyzed for safety.

3.3.3 *Full Analysis Set (FAS) Population*

All subjects who have had at least one dose of study drug and who have at least one evaluable post-dose PK sample will be included in the FAS Population. This population will be utilized for the PK analysis.

3.4 Subject Data and Study Conduct

3.4.1 *Subject Disposition*

Subject disposition will be presented for the Randomized Population. The number and percentage of subjects in each of the following categories will be summarized by treatment sequence and overall, as appropriate:

- Randomized;
- Dosed;
- Completed each treatment period;
- Completed the study;
- Prematurely discontinued the study and reasons for study discontinuation; and
- Prematurely discontinued the study due to COVID-19 pandemic.

3.4.2 *Protocol Deviations*

Protocol deviations will be summarized with frequency distributions (counts and percentages) by treatment sequence group and category for the FAS and Randomized Population. The denominators for calculating percentages will be based on the number of subjects in the FAS and Randomized Population for each treatment sequence group and overall.

Protocol deviations will be listed by treatment sequence for the Randomized Population.

3.4.3 *Analysis Populations*

Counts and percentages of subjects in each analysis population will be summarized by treatment sequence, formulation / condition and in total based on the Randomized Population.

3.4.4 *Demographics*

The following demographic and baseline characteristics will be listed and summarized by treatment sequence and formulation / condition with descriptive statistics or counts and percentages of subjects for the Randomized Population and repeated for all other analysis populations if they are different from the Randomized Population:

- Age (years)
- Sex
- Childbearing potential
- Ethnicity (Hispanic or Latino, Not Hispanic or Latino, Not reported, Unknown)
- Race (Asian, American Indian or Alaska Native, Black or African American, Native Hawaiian or Other Pacific Islander, White, Other)
- Height (cm)
- Weight (kg)
- Body Mass Index (BMI) (kg/m²)

3.4.5 *Medical History*

Medical history reported terms will be coded to system organ class and preferred term using the Medical Dictionary for Regulatory Activities (MedDRA) version 21.1. Medical history by system organ class and preferred term will be summarized by treatment sequence and in total for the Safety Population as well as listed

3.4.6 *Prior and Concomitant Medications*

Prior and concomitant medications will be coded with the World Health Organization Drug Dictionary Global B3 September 2018 version.

Prior medications will be defined as those medications (both prescribed and OTC) taken prior to the first dose of study drug in each treatment sequence. Medications taken at and after the time of first dose during the study will be defined as concomitant medications. Each treatment period will be defined as the period from the date and time of study drug dosing up to but not including the date and time of study drug dosing for the next treatment period (or end of study for the last treatment period). Concomitant medications taken at any time during a treatment period will be attributed to the corresponding treatment.

Concomitant medications will be summarized by formulation / condition for the Safety Population. All prior and concomitant medications will be listed.

3.5 Pharmacokinetic Assessment

3.5.1 *PK blood sampling*

PK samples were to be collected on Day 1 to Day 8, pre-dose and post-dose according to the PK Sample Schedule Group that the subject was assigned to.

On all four PK study days, all subjects will have baseline PK blood samples collected immediately prior to Ferric Maltol dosing (0 hr). Subjects will then have further PK blood samples collected at 11 additional times after dosing; the post-dose PK sample times will be 15 mins \pm 2 min, 30 mins \pm 2 min, 45 mins \pm 5 min, 1 hr \pm 5 min, 1.5 hr \pm 5 min, 2 hrs \pm 5 min, 3 hrs \pm 5 min, 4 hrs \pm 5 min, 6 hr \pm 10 min, 10 hrs \pm 15 min and 24 hrs \pm 15 min.

For each individual subject, the post-dose PK blood sampling schedule will be the same on all four PK days. PK blood samples on the PK days will be: serum iron, total and unsaturated iron binding capacity (TIBC, UIBC), transferrin, transferrin saturation (TSAT), maltol and maltol glucuronide.

3.5.2 *Handling missing PK data or concentration below the lower limit of quantification*

If the actual sampling time is missing, but a valid concentration value has been measured, the concentration value will be flagged, and the scheduled time point may be used for the calculation of PK parameters. If the dosing history information for a subject is missing, the sampling for that subject relative to the missing dose will not be included in the analysis.

Missing concentrations related to serum iron, TSAT, transferrin, TIBC, and UIBC will not be imputed or used in the analysis. If the dosing history information for a patient is missing, the sampling for that patient relative to the missing dose will not be included in the analysis.

For maltol and maltol glucuronide, all drug concentration below the quantifiable limit (BQL) are treated as zero. When more than half (>50%) of the values at a single timepoint are BQL, mean and median values are reported as BQL. Standard deviation and %CV are not reported; maximum and minimum values are reported as observed (including BQL). If, as the result of the calculation (eg. dose normalization, descriptive statistics) a concentration value is less than the LLOQ the value should be reported as <LLOQ value. The following general rules will be applied for the concentration summary (including tabulation and plotting) for each period:

- Mean concentrations at any individual time point will only be calculated if at least half of the subjects have valid values (i.e. quantifiable and not missing) at this time point for each formulation / condition.
- In cases where a mean value is not calculated, due to the above criterion not being met, the mean value will be set to missing for mean plotting purposes and to BLQ for summary table.
- BLQ will be set to zero for maltol and maltol glucuronide and to LLOQ for other analytes for the calculation of these mean values if applicable.

3.5.3 *PK Concentrations*

The observed values for maltol, maltol glucuronide, serum iron, baseline corrected serum iron, TSAT, TIBC, UBIC, and transferrin will be summarized by formulation / condition and by visit/timepoint for FAS Population using the following descriptive statistics: n (the number of subjects), arithmetic mean, standard deviation (SD), geometric mean, coefficient of variation (CV), median, minimum and maximum, and a 90% confidence interval (CI) for the mean.

The observed data for maltol, maltol glucuronide, serum iron (uncorrected and baseline corrected), TSAT, TIBC, UBIC, and transferrin will also be listed by formulation / condition group for each individual subject for FAS Population.

For maltol, maltol glucuronide, serum iron (uncorrected and baseline corrected), TSAT, TIBC, UBIC, and transferrin the mean observed plasma concentrations will be plotted on a linear and semi-logarithmic scale against nominal time range by formulation / condition. Geometric mean observed plasma concentrations and 90% CI will be plotted on a linear scale against nominal time range by formulation/condition. Individual observed concentrations be plotted on a linear and semi-logarithmic scale against actual timepoint for each formulation/condition.

3.5.4 *PK Parameters*

For serum iron, baseline corrected serum iron, maltol, maltol glucuronide, TSAT, TIBC, UBIC and transferrin, the following parameters will be calculated by non-compartmental analysis.

Parameters	Description
C_{\max}	Maximum plasma concentration directly from data
T_{\max}	Time to reach maximum concentration directly from data
λ_z	Apparent first-order terminal elimination rate constant (serum iron, maltol, and maltol glucuronide only)
$t_{1/2}$	Terminal elimination half-life, calculated as $\ln(2)/\lambda_z$ (serum iron, maltol, and maltol glucuronide only)
AUC_{last}	Area under the plasma concentration versus time curve from time zero to last.
AUC_{inf}	Area under the plasma concentration versus time curve from time zero extrapolated to infinity time (serum iron, maltol, and maltol glucuronide only)

The actual collection times will be used for the calculation of PK parameters. The Linear Up Log Down method (equivalent to the Linear Up/Log Down option in WinNonlin® Professional) will be used in the computation of AUC, if applicable.

The apparent terminal elimination rate constant (λ_z), will not be presented for subjects who do not exhibit a terminal elimination phase in their concentration-time profiles. In order to estimate λ_z , linear regression of concentration in logarithm scale versus time will be performed using at least 3 data points. Uniform weighting will be selected to perform the regression analysis to estimate λ_z .

Generally, the λ_z will not be assigned if one of the following happens:

1. T_{\max} is one of the 3 last data points,
2. The adjusted regression coefficient (R-squared) is less than 0.80,
3. The AUC_{extrap} exceeds 20%,
4. The estimated elimination rate indicates a positive slope, or
5. The terminal elimination phase is not linear (as appears in a semi-logarithmic scale) based on visual inspection.

If the λ_z is not assigned, the values of associated PK parameters (e.g. λ_z , AUC_{inf} , or $t_{1/2}$) will not be calculated.

Parameters will be listed by treatment sequence group for each individual subject and summarized by formulation/condition using the following descriptive statistics: n (the number of subjects), arithmetic mean, SD (standard deviation), geometric mean, geometric CV (coefficient of variation), median, minimum and maximum.

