3.2 Baseline

Baseline is defined as reading or measurements at Day 1 prior to study drug administration of each period. If the reading at Day 1 predose is missing, the last reading before first dosing will be set as baseline.

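### The SAP asks for geometric means and semi-log plots of baseline-corrected serum iron, a variable that can be zero or negative, and does not say whether the LLOQ rule acts before or after the baseline is subtracted

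*SAP*

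**What the plan says.** - **Variables and statistics (SAP 3.5.3).** "The observed values for maltol, maltol glucuronide, serum iron, baseline corrected serum iron, TSAT, TIBC, UBIC, and transferrin will be summarized" by formulation/condition and time point. The statistics include the arithmetic mean, geometric mean, CV and a 90% CI for the mean. Mean profiles are drawn on linear and semi-logarithmic scales. In addition, "Geometric mean observed plasma concentrations and 90% CI will be plotted on a linear scale against nominal time range by formulation/condition".
- **Baseline (SAP 3.2).** "Baseline is defined as reading or measurements at Day 1 prior to study drug administration of each period". Each period therefore has its own baseline. No formula for the correction appears in either document.
- **Values below the limit (SAP 3.5.2).** "Mean concentrations at any individual time point will only be calculated if at least half of the subjects have valid values" (quantifiable and not missing). Otherwise "the mean value will be set to missing for mean plotting purposes and to BLQ for summary table". For the means that are calculated, "BLQ will be set to zero for maltol and maltol glucuronide and to LLOQ for other analytes", where applicable. An earlier paragraph of 3.5.2, which opens with maltol and maltol glucuronide, says that where the result of a calculation gives a value such that "a concentration value is less than the LLOQ the value should be reported as <LLOQ value".
- **Protocol.** The synopsis (Statistical Methods) includes baseline-corrected serum iron among the analytes summarised with a geometric mean, and asks for geometric-mean plots with 90% CI. Section 12.2 leaves corrected iron out of its list of concentration summaries.
- **Role.** Corrected iron is the second secondary PK endpoint (SAP 2.3.2). The primary endpoints use total serum iron (SAP 2.3.1).

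**The concern.** A geometric mean and a log axis need strictly positive values. Under subtraction, baseline-corrected iron is exactly 0 at pre-dose in every profile that has a pre-dose sample. It falls to zero or below whenever serum iron returns to, or drops under, its pre-dose level. The SAP has no rule for such values, so the programmer would have to choose between omitting the statistic, dropping the values and substituting something positive, possibly after seeing the data. The last two choices push the summary upward.

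The LLOQ rule adds a second ambiguity. An LLOQ is a limit on an assayed concentration, and corrected iron is a difference. If the rule is applied to the difference, every zero or negative change is replaced by a positive number in the mean.

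At stake is how far the mean profiles of the variable meant to isolate iron from the dose can be trusted, mainly at the later sampling times (6, 10 and 24 h).

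**Working it through.** The plan states no figure to reproduce: it gives no LLOQ, no SD of corrected iron and no expected late mean. What follows is an illustration.

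**Inputs**
- From the SAP: 32 subjects per formulation/condition (2.2.1; each subject receives all four); a mean is shown if at least half have quantifiable values (3.5.2).
- Assumed: corrected values at a time point are normal with mean m and SD s of 20 to 40 ug/dL; LLOQ L of 2 to 10 ug/dL.

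**1. Can the geometric mean be computed?** The chance of at least one value at or below zero among 32 is 1 − Φ(m/s)^32.
- m = +1 SD: 1 − 0.8413^32 = 0.996.
- m = +0.5 SD or lower: above 0.999.

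Even where mean iron is well above baseline, the statistic is almost always undefined without a further rule.

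**2. Non-positive values dropped, m = 0.** The geometric mean of the positive half of N(0, s²) is s × exp(−(0.5772 + ln 2)/2) = s × exp(−0.635) = 0.530 s.
- s = 20: 10.6
- s = 30: 15.9
- s = 40: 21.2

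The true mean is 0.

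**3. LLOQ rule applied to the corrected value.** With a = (L − m)/s, the expected arithmetic mean after substitution is E = L·Φ(a) + m·(1 − Φ(a)) + s·φ(a). The expected share below LLOQ is Φ(a). The chance that a mean is shown is P(Binomial(32, 1 − Φ(a)) ≥ 16).

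Lowest and highest case at m = +10:
- s = 20, L = 2: a = −0.4; E = 2 × 0.3446 + 10 × 0.6554 + 20 × 0.3683 = 0.69 + 6.55 + 7.37 = 14.6.
- s = 40, L = 10: a = 0; E = 10 × 0.5 + 10 × 0.5 + 40 × 0.3989 = 5 + 5 + 15.96 = 26.0.

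| True mean m (ug/dL) | Share below LLOQ | Mean after substitution | Chance a mean is shown |
|---|---|---|---|
| +10 | 34–50% | 14.6–26.0 | 57–98% |
| 0 | 52–69% | 9.0–21.5 | 2–48% |
| −20 | 71–93% | 3.4–15.2 | about 1% or less |

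The third column averages over all samples. Showing a mean only when enough values are quantifiable selects higher samples and adds a little more upward shift.

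**4. Pre-dose under the same reading.** All values are 0, so none of 32 is quantifiable. The mean is missing in the plot and BLQ in the table; LLOQ is not plotted.

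**5. LLOQ rule applied only to assayed iron before subtraction.** If no assayed serum iron value is below LLOQ, nothing is substituted and the arithmetic mean has no bias. Steps 1 and 2 still apply to the geometric mean.

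**The case against.** The strongest reply is that an LLOQ belongs to an assay. Corrected iron is not assayed, the substitution rule is limited to cases where it applies, and the sentence on calculated values sits in a paragraph about maltol and maltol glucuronide and governs reporting only. On that reading the arithmetic means are unbiased. This stands as a possible reading, but the SAP does not choose it: 3.5.3 lists corrected iron alongside the assayed analytes, and the sentence on calculated values can be read to reach derived quantities.

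A reader might go further and infer that the late mean profiles are biased upward as a matter of course, would show iron above baseline at 10 to 24 h when it is not, and so overstate the duration of absorption. The documents do not support that. It needs the rule to act on the difference, and even then the half-of-subjects requirement leaves most means centred at or below zero unshown. Displayed bias arises mainly where the true corrected mean is still positive.

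It is also fair to say that the effect is descriptive. The means feed neither the NCA parameters nor the ANOVA of SAP 3.5.5, no formulation comparison by time point is planned, and individual listings and plots are required as well. The table, figure and programming specifications are separate documents not available here and may contain a rule. All of this limits the weight of the point. None of it makes a geometric mean of zero or negative values computable.

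**Conclusion.** The point holds in a limited form. With subtraction of each period's own pre-dose value, the geometric means, their 90% CIs and the semi-log plots that SAP 3.5.3 requires for baseline-corrected iron cannot be produced as written. If non-positive values are dropped, they are biased upward, by about 11 to 21 ug/dL at a true mean of 0 and SD of 20 to 40.

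Upward bias of the arithmetic mean is conditional on a reading that the SAP leaves open. Under that reading, a true mean of +10 would display as about 15 to 26 (LLOQ 2 to 10), while means at or below 0 would mostly appear as missing or BLQ. The SD, LLOQ, true means and normal shape are all assumptions, so these figures show direction and rough scale only.

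The consequence is confined to the descriptive concentration tables and plots of a secondary variable. A reader might infer a threat to the conclusion on interchangeability of the two products; there is none from this rule, because the primary endpoints use total serum iron and the ANOVA uses subject-level parameters.

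**What to change.** **SAP 3.5.2.** Define baseline-corrected serum iron as the observed value minus that period's pre-dose value. State that LLOQ handling applies to assayed serum iron before subtraction only, and that corrected values keep their sign, zero and negative included, in listings, tables and plots.

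**SAP 3.5.3.** For baseline-corrected iron, remove the geometric mean, its 90% CI and the semi-log plots. Show the arithmetic mean with 90% CI and the median, on the linear scale.

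**Record of change.** Note this in the SAP as a departure from the protocol synopsis, which asks for geometric means of this variable.

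**Cost.** A few sentences and one changed table and figure shell before database lock, with no new data. The downside is that one variable is displayed differently from the others. This change does not settle how non-positive corrected values enter AUC_last or the log-down step in SAP 3.5.4; that is a separate question, best answered in the same revision.

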3.5.5 PK analysis

To compare the pharmacokinetics of ferric maltol capsules and oral suspension under fasted and fed conditions, a subject must have a calculable PK parameter for both formulations under fasted or fed condition.

An ANOVA model will be performed on the ln-transformed PK parameters (C_{\max} , AUC_{last} and AUC_{inf}) of the two formulations including terms for sequence (treatment sequence), treatment (formulation/condition), and period as fixed effects, and subjects nested within a sequence as a

random effect. The estimates will be back-transformed into original scale. The point estimates for ratios and the corresponding 90% CIs will be provided.

The PK parameters analyses will be based on the FAS Population.

The sample SAS code for this analysis is included here for $\alpha = 0.10$:

```
proc mixed;
  class subject treatment sequence period;
  model logPKvar = treatment sequence period /ddfm=Satterthwaite; random
  subject(sequence);
  lsmeans treatment/pdiff cl alpha=0.1;
  run;
```

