The sample size is based on the comparisons of each of the primary PK parameters C_{max} and AUC_{last} for total serum iron between the formulations for each of the two conditions: fed and fasted. Each comparison will be made via the ratio of the two values of the parameter between the formulations. The 90% confidence interval (CI) for this ratio will be reported.

Thus, there are 4 primary endpoints:

In fed condition

C_{max} (suspension) / C_{max} (capsule)

AUC_{last} (suspension) / AUC_{last} (capsule)

In fasted condition

C_{max} (suspension) / C_{max} (capsule)

AUC_{last} (suspension) / AUC_{last} (capsule)

Data from a previous study (ST10-01-101) were used to provide estimates of the standard deviations (SDs) of the logs of the within-subject ratios of the parameters C_{max} and AUC_{last} (between formulations). Assuming the SD is no greater than 0.38, and that the true ratio is 1, 20 subjects would provide a probability of at least 80% of each individual confidence interval lying

within (80%, 125%). Further if all the 4 ratios to be reported are independent, 31 subjects would provide probability of at least 80% of all 4 confidence intervals lying within (80%, 125%). As the SD is uncertain, 32 subjects will be recruited in the study.

The target recruitment number is 32 and up to an additional 4 may be recruited to replace early withdrawing subjects.

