2.3.2 Secondary PK Endpoints

1. PK analysis of total serum iron concentration; AUC_{inf} in fasted and fed conditions
2. PK analysis of baseline corrected serum iron concentration; C_{max} , AUC_{last} , AUC_{inf} in fasted and fed conditions
3. PK analysis of maltol and maltol glucuronide in plasma; C_{max} , AUC_{last} in fasted and fed conditions
4. PK analysis of TSAT, TIBC, UIBC, transferrin; C_{max} , AUC_{last} in fasted and fed conditions

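### No rule covers zero or negative baseline-corrected iron AUC, so the ln analysis of this secondary endpoint drops an unknown, non-random share of values

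*SAP*

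**What the plan says.** SAP 2.3.2 lists "PK analysis of baseline corrected serum iron concentration" (Cmax, AUClast and AUCinf, fasted and fed) among the secondary endpoints. SAP 3.2 takes as baseline the pre-dose reading of each period. SAP 3.5.4 derives non-compartmental parameters for corrected iron alongside the other analytes.

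SAP 3.5.5 then says "An ANOVA model will be performed on the ln-transformed PK parameters", and that for the comparison "a subject must have a calculable PK parameter for both formulations under fasted or fed condition". It does not name the analytes. The Protocol does: the statistical methods in its synopsis commit corrected iron to within-subject ratios summarized by a geometric mean and 90% CI, and Protocol 12.2 plans such ratios for each analyte.

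Two handling rules come near the problem without reaching it. Missing data are not imputed (SAP 3.1.3). The substitution rule in SAP 3.5.2 reads, up to its closing qualifier, "BLQ will be set to zero for maltol and maltol glucuronide and to LLOQ for other analytes for the calculation of these mean values if". It concerns mean concentrations at a time point, not PK parameters.

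**The concern.** Corrected iron is the endpoint closest to absorbed iron. After subtraction, any sample below that period's pre-dose value is negative, and a profile with little absorption, a high pre-dose value or a fall in iron over the day can have a total area at or below zero. Its logarithm does not exist, so the mixed model drops the record without comment. The Protocol's geometric-mean ratios have the same gap.

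The loss is informative, because it depends on the size of the outcome itself. If the formulations differ, the lower-absorbing one loses more values, and the ratio is estimated on a selected subset. At stake are a possibly biased ratio, a 90% CI that may not have its nominal coverage, and handling chosen after open-label data have been seen.

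**Working it through.** **Inputs from the documents.** Twelve samples per period, from pre-dose to 24 h, with none between 10 and 24 h; 32 subjects; baseline is one pre-dose value per period; "The 90% confidence interval (CI) for this ratio will be reported"; log-ratio SD at most 0.38. **Not in the documents, so assumed and varied:** the corrected signal relative to its noise, between-day variation, within-day fall in iron, and the convention for negative values.

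**The plan's own figures.** SAP 2.2.4 says "Assuming the SD is no greater than 0.38, and that the true ratio is 1, 20 subjects would provide a probability of at least 80" per cent for each interval, and "31 subjects would provide probability of at least 80% of all 4 confidence intervals lying within (80%, 125" per cent). With n = [0.38 x (z0.95 + z_power) / ln 1.25]^2:
- power 0.80: [0.38 x (1.645 + 0.842) / 0.2231]^2 = 17.9, so 18 (20 with the t distribution);
- power 0.80^(1/4) = 0.946: [0.38 x (1.645 + 1.605) / 0.2231]^2 = 30.6, so 31 (33 with t).

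Both reproduce approximately with this formula, which tests one limit only (a separate matter). They concern total iron. No figure in the plan describes corrected iron.

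**Step 1: can the area be non-positive?** Take an illustrative absorption curve at the Protocol's sampling times plus a within-day fall of 3 units, which contributes -37.0 to the 0-24 h area (arbitrary units):
- peak 2: 18.5 - 37.0 = -18.5; with negatives set to zero, +3.7;
- peak 5: 46.2 - 37.0 = 9.2; with negatives set to zero, 20.7;
- peak 10: 92.3 - 37.0 = 55.3; unchanged with negatives set to zero.

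So it can, and the unstated convention decides whether the first profile is lost. Corrected Cmax cannot be negative if the 0 h value is included; in the peak 2 case it is 1.08.

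**Step 2: what the ln step does.** Let corrected AUC = absorption + normal noise (SD 1), with capsule mean m and suspension mean r x m. The share of pairs lost is 1 - Phi(m) x Phi(r x m). For r = 0.80 and m = 1 this is 1 - 0.841 x 0.788 = 0.337. The reported ratio is exp(E[ln S | S > 0] - E[ln C | C > 0]):
- true 0.80: 0.88 (34% of pairs lost), 0.83 (17%), 0.79 (8%), 0.77 (1%) at m = 1, 1.5, 2, 3;
- true 0.60: 0.78 (39%), 0.62 (13.5%), 0.56 (4%) at m = 1, 2, 3;
- true 1.00 with equal noise: 1.00 throughout;
- true 1.00 with noise SD 1.5 against 1: 1.22 (37%), 1.10 (21%).

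With equal noise, the bias changes sign at about 9-10% of pairs lost: towards 1 above that, and away from 1 below it, where small positive values dominate on the ln scale.

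**Step 3: is the both-formulations condition the cause?** The SAP mixed model over the four sequences, true ratio 0.80, gave 0.866, 0.805 and 0.782 with the condition (34%, 20% and 8% of pairs lost). It gave 0.881, 0.816 and 0.788 when only the non-positive records were deleted. The ln step causes the loss; the condition adds nothing to the pull towards 1.

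**Step 4: how much depends on convention?** Simulations on the Protocol's sampling times assumed pre-dose iron of 100, a rise of 30 or 60, and a between-day log SD of 0.10 or 0.20 (0.38 / sqrt 2 = 0.27 is the per-period value that the plan's bound would allow).
- Negatives kept, no within-day fall, paired log-ratios: true 0.50 left 17.6-27.1 of 32 pairs, with a reported ratio of 0.54-0.73 and 90% CI coverage of 69-87%.
- Further runs with negatives kept: 3-45% of pairs lost with no within-day fall and 40-93% with a 20% fall; true 0.80 reported as 0.73-0.90.
- Negatives set to zero: loss of about 1% or less, but true 0.70 still became 0.72-0.75 and true 0.50 became 0.53-0.59.
- Corrected Cmax: at most about 1.3% of pairs had a value at or below zero.

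**Step 5: what works without a logarithm?** Use the areas of step 1, negatives kept, true ratio 0.80:
- peak 2: difference 14.8 - 18.5 = -3.7; ratio of means (14.8 - 37.0) / (18.5 - 37.0) = 1.20;
- peak 5: difference 37.0 - 46.2 = -9.2; ratio (37.0 - 37.0) / 9.2 = 0.00;
- peak 10: difference 73.8 - 92.3 = -18.5; ratio (73.8 - 37.0) / 55.3 = 0.67.

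A fall common to both formulations cancels from the difference, which stays at 20% of the capsule's absorbed area. It does not cancel from the ratio. In simulation with a 20% fall, the ratio of untransformed means came out at 0.48 to 2.0 for true 0.80, and at -0.28 to 3.6 for true 0.50.

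**The case against.** A reader might infer that the analysis pulls the ratio towards 1 and so favours interchangeability. The documents do not support that. The direction varies with the loss and the noise (step 2). Protocol 12.1 rests the aim on four total-iron intervals, and corrected iron has no acceptance limits. In simulations with a true ratio of 0.70 or 0.50, the corrected interval fell within 80-125% in at most 0.1% of trials. A reader might also blame the both-formulations condition; step 3 shows otherwise, and a negative AUC is arguably still calculable.

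The size is open to challenge too. The larger biases assume that negatives are kept and that the 24 h sample has its own day effect, and the 10-24 h interval is 14 of the 24 hours. Without that day effect, true 0.50 at the larger rise was reported as 0.50-0.51 with 89% coverage. That stands: no size can be claimed for this trial.

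Finally, SAP 3.5.5 names no analytes, and SAP 6 defers programming detail to a separate document that may hold a rule. But the Protocol commits corrected iron to geometric-mean ratios, which need positive values as well, and a choice that decides who is analysed belongs in the SAP.

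**Conclusion.** The gap is real and confined to a secondary endpoint. As written, the analysis of corrected iron AUC loses any non-positive value, non-randomly, and no rule in either document prevents it. With equal formulations and equal noise there is no bias, only fewer subjects. When the formulations differ, or their noise differs, the ratio can be biased either way. The loss ranges from about 1% or less to most pairs, depending on the negative-value convention, the noise and the within-day fall, none of which the documents give. That sensitivity is itself the reason to settle the rule before database lock. The conclusion also assumes that correction means subtracting the period's 0 h value and that SAP 3.5.5 applies to corrected iron; both are the natural reading but are not stated. It is worth correcting, but it does not threaten the primary analysis.

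**What to change.** - In SAP 3.5.4-3.5.5, state the correction (value minus that period's 0 h value), one rule for negative corrected concentrations, and a fixed 0-24 h window for corrected AUC.
- Keep the ln-ANOVA for corrected parameters, but report, by formulation and condition, the number of values at or below zero and of pairs excluded.
- Add a supportive analysis: the same model fitted to untransformed corrected AUC, with negative areas and all subjects kept, reporting the suspension-minus-capsule difference of LS means with a 90% CI for each condition. Give a ratio of means with a Fieller interval only where the capsule mean is clearly above zero (step 5).
- In SAP 3.5.3, replace the geometric mean of corrected concentrations by time point with the arithmetic mean and 90% CI; at 0 h the corrected value is zero by construction, so its geometric mean is zero or undefined.
- Leave the total-iron analysis unchanged.

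The cost is some SAP text, a few lines of code and one extra table, with no new data. The drawback is that the difference is in concentration-time units rather than on the ratio scale used elsewhere.
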